7.1 Subject Disposition

Subject Disposition will be describe with a figure following CONSORT statement¹ including all the subjects enrolled, subjects that received recombinant human erythropoietin by treatment group (HEMAX® PFS or EPREX/ERYPO), withdrawn subjects and reason for withdrawal (such as Transfusion, Adverse Event, Lack of efficacy or withdrew consent).

7.2 Protocol Deviations

The study team throughout the conduct of the study will track all the protocol deviations and they will be notified to the Ethic Committees and/or regulatory authorities, either in immediate reports, or in the periodic reports if it is required. Risk for patient’s safety will be evaluated for each deviation.

Major deviations which could result in exclusion from the per-protocol analysis population will also be summarized and listed. These deviations are:

- Eligibility Criteria Not Met
- Non-compliance with randomized medication and/or wrong study treatment or assignment administered before week 12
- Lack of evaluable Hb value corresponding to primary endpoint at week 12

7.3 Demographic and Baseline Variables

The following data will be collected and summarize: Sex (male/female, number and percentage) Age (years, median, and range) Weight (kg, mean \pm SD) Height (m, mean \pm SD) Body Mass Index (mean \pm

SD), probable cause for kidney disease by treatment group (such as Diabetes, Arterial Hypertensión, Systemic Erythematosus Lupus, other causes for nephritis, Para-infectious Glomerulopathy)

7.4 Concurrent Illnesses and Medical Conditions

The concurrent illnesses and medical conditions will be describe using MedDRA

7.5 Prior and Concurrent Medications

Prohibited Medications:

Transfusions: Patients will be transfused according to the clinical judgment of the investigator, based on the patient's symptoms and not on a cutoff value of hemoglobin. The transfused patients will be withdrawn from the study for having reached a study endpoint.

Permitted medications

Iron intake: All patients will receive concomitant treatment with iron orally to maintain the levels of transferrin saturation >20% according to the indications of the treating physicians. The intravenous iron is also permitted, according to the criterion of the treating physicians

Other data to be collected related to prior and concomitant medications are:

- Number of patients with anemia that had received treatments previously and number of treatments received previously by each patient
- Other concomitant medication administered to the randomized patients not specific for anemia (such as hypertension or diabetes).

7.6 Treatment Compliance

The patients should return to the center all the containers with the drug product used during the study, and all the medications that they had not used during the study. The staff in the center recorded in the source document and on the patient accountability individual record, the patient number, and the number of returned containers.

During the study, the monitor checked continuously all the containers with the study medication (used, and non-used containers), and the corresponding accountability forms. At the same time, at each visit the card in which the patient recorded the date and drug product dose administered, is checked. Accountability records of the drug products used during the study were kept in the centers all the time. At the moment the study was ended a final accountability was carried out and all the remnant medication was withdrawn for destruction, as stated in current regulations. .

The following measures will de obtained related to treatment compliance:

- Epoetin dose (IU) administered every week in each group (mean \pm SD): Mean for cumulative doses per patient at the titration stage, maintenance stage, and during the whole treatment
- Number of patients that suspended the treatment at each visit

8 Efficacy Analyses

All efficacy variables will be listed by subject within study site. Data will be summarized by treatment group. Number and percentage will summarize categorical efficacy variables and Number, Mean, Standard Deviation, Minimum and Maximum will summarize continuous efficacy variables, whereas.

Inferential statistics will be performed through intergroup analysis analysis using ANCOVA covariance analysis comparing each treatment group (patients treated with HEMAX PFS versus those treated with EPREX/ ERYPO®) or the statistical “t” Student test for independent samples considering 5% significance level.

An additional intragroup analysis evaluating the variations in hemoglobin (increase from baseline to the average of the visits between weeks 8 and 12) adjusted for the baseline value, using a significance level of 5% will be performed

The assumptions regarding normality and homogeneity will be checked.

8.1 Primary Efficacy Analysis

The primary efficacy analysis will be performed for Per Protocol population.

The primary efficacy assessment will be carried out through the levels of hemoglobin increase from baseline value to the mean value of the visits between week 8 and 12, comparing patients treated with HEMAX PFS versus those treated with EPREX/ ERYPO®.

Additionally, treatment equivalence will be established if the difference between the two groups excludes a difference between treatment groups greater than 1g/ dl in hemoglobin increase from baseline value to the mean value of the visits between week 8 and 12 with a difference in the mean dose of epoetin alfa in these visits no greater than 20%.

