9.4 EARLY TREATMENT TERMINATION

The termination visit should be performed in all patients that completed the study prematurely. Patients who decide not to continue with the visits must perform the termination visit before completion. A patient may leave or be excluded from the study due to the following reasons:

- Death.
- Adverse event that in the opinion of the investigator requires early withdrawal (specify principal AE in the AE form).
- Revocation of informed consent.
- At the request of the investigator or physician primarily responsible for the care of the patient.
- Due to major protocol violation that required discontinuation.
- Loss of follow - up, including the fact that patient does not return to the site.
- Positive pregnancy test at any time during the study.
- Patient transfusion or lack of response after 12 weeks of treatment.
- If after twelve weeks the hemoglobin did not increase during the titration phase by at least 1 g/dL from baseline, the patient will be withdrawn from the study.

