16.3.1 Full Analysis Set (FAS)

The full data analysis group will consist of all patients enrolled in this study that have been randomized and who have received at least one dose of the study medication.

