16.3.2 Per Protocol (PP) analysis group

The per protocol data analysis group will consist of all patients enrolled in this study who have received at least one dose of the study medication, who have completed at least one follow - up visit and that do not have major protocol violations.

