16.5 EFFICACY ANALYSIS

The efficacy analysis will be performed for both FAS and PP populations. Descriptive statistics and inferential statistics will be performed through intergroup analysis (ANCOVA covariance analysis)-comparing each treatment group (patients treated with HEMAX PFS versus those treated with EPREX/ERYPO®) and an additional intragroup analysis analyzing the variations in hemoglobin (increase from baseline to the average of the visits between weeks 8 and 12) adjusted for the baseline value, using a significance level of 5%. Statistical analysis will be performed with SPSS software or equivalent.

The following parameters will be evaluated for treatment efficacy, according to the objectives defined by the protocol.

The **primary efficacy assessment** will be carried out through the levels of hemoglobin increase from baseline value to the mean value of the visits between week 8 and 12, comparing patients treated with HEMAX PFS versus those treated with EPREX/ERYPO®.

Additionally, **treatment equivalence** will be established if the difference between the two groups excludes a difference between treatment groups greater than 1g/ dl in hemoglobin increase from baseline value to the mean value of the visits between week 8 and 12 with a difference in the mean dose of epoetin alfa in these visits no greater than 20%.

The **secondary efficacy assessment** will be carried out through the evaluation of the following objectives:

- Percentage of responder patients (increase of Hb \geq 1g/ dl) after 12 weeks of treatment, comparing patients treated with HEMAX PFS versus those treated with EPREX/ERYPO®.

- Percentage of transfusion requirement after 12 weeks of treatment, comparing patients treated with HEMAX PFS versus those treated with EPREX/ ERYPO®.
- Intragroup efficacy (HEMAX PFS and EPREX/ ERYPO®) of treatment with Epoetin Alfa through increased levels of hemoglobin from baseline in each one of the intermediate visits until the week 12 visit.
- Evaluate the intragroup efficacy (HEMAX PFS and EPREX/ ERYPO®) of the change from the twice - a - week dosing during the titration phase to a weekly dosing during the maintenance phase through the variation of the hemoglobin levels from week 12 to the weeks 16, 20 and 24.

For **missing hemoglobin data**, the last observation carried forward method will be used.

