6.2 Analysis Populations

6.2.1 Per Protocol Population

- All subjects who received any study drug and who completed at least week 12 follow up visit to evaluate primary efficacy endpoint and who did not substantially deviate from the protocol.

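### The SAP drops the protocol's FAS efficacy analysis and confines the primary comparison to week-12 completers, which removes patients transfused or otherwise withdrawn before week 12

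*SAP*

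**What the plan says.** Protocol 16.5 states: "The efficacy analysis will be performed for both FAS and PP populations". Protocol 16.3.1 defines the FAS as "all patients enrolled in this study that have been randomized and who have received at least one dose of the study medication". Beyond one dose, the protocol's PP set (16.3.2) asks only for patients "who have completed at least one follow - up visit and that do not have major protocol violations".

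The SAP defines two populations, Per Protocol (6.2.1) and Safety (6.2.2). A safety FAS is mentioned once, in 9.1, as an adverse-event denominator; it is not defined and has no efficacy role. SAP 8.1 reads: "The primary efficacy analysis will be performed for Per Protocol population". SAP 6.2.1 restricts that population to those "who completed at least week 12 follow up visit to evaluate primary efficacy endpoint", and SAP 7.2 lists "Lack of evaluable Hb value corresponding to primary endpoint at week 12" among the major deviations that could lead to exclusion.

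On withdrawal, SAP 7.5 says: "The transfused patients will be withdrawn from the study for having reached a study endpoint". Protocol 9.4 and 11.3 say the same. Protocol 9.4 also lists adverse events, withdrawn consent and loss to follow-up as reasons for leaving, and withdraws non-responders under the condition "If after twelve weeks the hemoglobin did not increase during the titration phase by at least 1 g/dL from baseline".

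Both documents use LOCF for missing haemoglobin (Protocol 16.5, SAP 6.3). SAP 8.2 names no population for the responder and transfusion endpoints. SAP 12, the summary of protocol changes, does not mention the change of population.

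**The concern.** Membership of the only primary population now depends on what happens after randomisation, and part of what removes a patient is treatment failure: the SAP itself calls transfusion a study endpoint. The trial is open-label, and transfusion follows the investigator's judgement rather than a haemoglobin cutoff. If early exits differ between arms in number or in haemoglobin response, the completers' difference can depart from the all-treated difference in either direction.

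Three features make this serious here:

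- **Size.** The trial enrolled 43 patients (23 vs 20) against 120 planned, so a few early exits can decide whether the confidence interval stays inside 1 g/dL.
- **No cross-check.** The protocol's FAS analysis would have exposed such a discrepancy, and the SAP removes it.
- **Timing.** SAP 5 already reports interim results and final enrolment, so a narrower primary set than the protocol's needs a stated, dated reason. The text does not show when or why the set was narrowed, and no motive should be inferred.

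**Working it through.** **Step 1. The definitions side by side**

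| | Protocol | SAP |
|---|---|---|
| Efficacy sets | FAS and PP (16.5) | PP only for the primary analysis (8.1) |
| FAS | Randomised and dosed (16.3.1) | Not defined |
| PP visit requirement | At least one follow-up visit (16.3.2) | Week-12 visit completed (6.2.1); evaluable week-12 Hb (7.2) |
| Missing Hb | LOCF (16.5) | LOCF (6.3) |

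**Step 2. Who is removed**

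- Transfused before week 12: withdrawn by rule, so no week-12 visit and not in the SAP's PP set.
- Adverse event, withdrawn consent or loss to follow-up before week 12: also out.
- Rise below 1 g/dL: withdrawn after the week-12 assessment, so still in PP if a week-12 Hb exists and there is no other major deviation.
- LOCF cannot act for anyone who leaves before week 12. At most it fills a missed week 8 or week 10.

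**Step 3. How far this can move the result**

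The documents give no figure that settles this. N = 120 cannot be reproduced because no SD is stated, so what follows is illustration.

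Inputs from the documents: 23 HEMAX PFS and 20 EPREX/ERYPO (SAP 5), margin 1 g/dL and two-sided 5% level (SAP 3.2.4). Assumed: early withdrawals kT and kR; mean change in completers cT and cR; mean change at last value in withdrawn patients w = -0.3 g/dL; within-group SD; all 43 patients dosed.

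- FAS difference = [(1 - kT/23)cT + (kT/23)w] - [(1 - kR/20)cR + (kR/20)w]
- PP difference = cT - cR
- FAS variance per arm = SD² + f(1 - f)(c - w)², with f = k/n, pooled over arms
- 95% t intervals use n = 23, 20 for FAS and 23 - kT, 20 - kR for PP

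Case 1 in full (5 vs 1 withdrawn, completers +1.3 in both arms, SD 1.2):

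- HEMAX PFS mean = (18/23)(1.3) + (5/23)(-0.3) = 0.952. EPREX/ERYPO mean = (19/20)(1.3) + (1/20)(-0.3) = 1.220. FAS difference = -0.27; PP difference = 0.
- FAS variances: 1.44 + 0.436 = 1.876 and 1.44 + 0.122 = 1.562. Pooled SD 1.315. Half-width = 2.020 × 1.315 × √(1/23 + 1/20) = 0.81. CI -1.08 to 0.54.
- PP half-width = 2.030 × 1.2 × √(1/18 + 1/19) = 0.80. CI -0.80 to 0.80.

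| Case | Withdrawn | Completers (g/dL) | SD | PP difference (95% CI) | FAS difference (95% CI) |
|---|---|---|---|---|---|
| 1 | 5/23 vs 1/20 | +1.3 both | 0.8 | 0 (±0.53) | -0.27 (-0.86 to 0.33) |
| 1 | 5/23 vs 1/20 | +1.3 both | 1.0 | 0 (±0.67) | -0.27 (-0.97 to 0.43) |
| 1 | 5/23 vs 1/20 | +1.3 both | 1.2 | 0 (±0.80) | -0.27 (-1.08 to 0.54) |
| 1 | 5/23 vs 1/20 | +1.3 both | 1.5 | 0 (±1.00) | -0.27 (-1.25 to 0.72) |
| 2 | 7/23 vs 1/20 | +1.3 both | 1.0 | 0 (±0.69) | -0.41 (-1.12 to 0.31) |
| 3 | 1/23 vs 5/20 | +1.3 both | 1.0 | 0 (±0.68) | +0.33 (-0.37 to 1.03) |
| 4 | 1/23 vs 4/20 | +0.5 vs +1.3 | 1.0 | -0.80 (-1.47 to -0.13) | -0.52 (-1.19 to 0.16) |
| 5 | 3/23 vs 3/20 | +1.3 both | 1.0 | 0 (±0.67) | +0.03 (-0.67 to 0.74) |

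Case 4 shows that PP can also look worse than FAS. When completers do equally well, each early withdrawal moves the all-treated difference by 1.6/23 = 0.07 g/dL (HEMAX PFS) or 1.6/20 = 0.08 g/dL (EPREX/ERYPO).

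**Step 4. Secondary endpoints**

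If the SAP's PP set were also used for SAP 8.2, transfusion before week 12 would be about 0% in both arms by construction, and the responder percentage would omit those patients. The SAP does not say that it will be used; the population is simply not named.

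**The case against.** PP is a recognised analysis for equivalence, and a completers' set avoids carrying early values forward. Early exits would not be hidden: SAP 7.1 plans a CONSORT figure with withdrawals and reasons, and SAP 7.6 counts patients suspending treatment at each visit.

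The illustrated reversals also depend on the inputs:

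- With w = +0.3, plausible for later exits because Protocol 4.3 puts the usual rise at 2 to 6 weeks, the FAS intervals in case 1 (SD 1.2) and case 2 stay inside the margin: -0.94 to 0.60 and -0.91 to 0.40.
- With w = 0 they are only just outside, with lower limits of -1.01 and -1.02.
- With a 90% interval (two one-sided 5% tests), case 1 at SD 1.2 gives -0.94 to 0.41, inside.
- With SD 1.69, the value implied by 60 per arm at 80% power with two one-sided 2.5% tests and no true difference (√30/(1.960 + 1.282)), the case 1 PP interval is ±1.13. PP then fails as well and nothing reverses.

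Finally, the protocol asks for both analyses but does not say that both must succeed.

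All of this is correct, and it limits what can be said about size. It does not remove the conflict between the documents. A disposition figure shows who left but does not estimate the treatment difference with those patients included. PP is a companion analysis in the protocol, not a replacement. If few patients left early, the FAS costs little and will confirm PP.

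**Conclusion.** The concern holds. The protocol requires FAS and PP; the SAP keeps PP alone, narrows it to week-12 completers, and gives no justification. As written, it removes patients transfused or otherwise withdrawn before week 12 from the only primary population. This rests on the text and needs no assumption.

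The effect on the estimate is unknown in size and direction. In the equal-completer illustrations with unequal withdrawals it is 0.27 to 0.41 g/dL in absolute value, enough to change the equivalence conclusion at some plausible SDs and not at others; with balanced withdrawals it is 0.03. Those figures depend on assumed withdrawal counts, SD and last values. The point must be fixed because an analysis of the primary endpoint that the protocol requires is missing and, at 43 patients, could alter the conclusion.

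**What to change.** Needed:

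1. Define the FAS in the SAP as in Protocol 16.3.1. Report the Hb equivalence analysis in FAS and PP, and conclude equivalence only if they agree. The agreement rule goes beyond the protocol's wording.
2. Return PP to the protocol definition, or justify the week-12 condition as a dated change and label that set a completers analysis.
3. State the FAS data rule. Use Hb up to withdrawal or transfusion and exclude values taken after a transfusion, so that a termination-visit value raised by transfusion is not carried forward. For patients with no week 8-12 Hb, apply the existing LOCF rule to the last pre-transfusion value, or to baseline (change 0) if there is none, and report the number by arm.
4. Name FAS as the population for the responder and transfusion endpoints in SAP 8.2. Count patients transfused or withdrawn before week 12 as non-responders, and every transfusion as an event.
5. Add a week-12 cut, by arm and reason, to the withdrawal summary already planned in SAP 7.1.

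Useful in addition, because LOCF from early exits is itself an assumption: a sensitivity analysis using a repeated-measures model of all visits to week 12, contrasting the average of weeks 8, 10 and 12 between arms.

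Cost: SAP wording, one more set of efficacy tables, and one model if the sensitivity analysis is added. No new data are needed. The FAS result may be less favourable than PP.

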8.2 Secondary Efficacy Analyses

- Percentage of responder patients (increase of Hb \geq 1g/ dl) after 12 weeks of treatment, comparing patients treated with HEMAX PFS versus those treated with EPREX/ ERYPO®.
- Percentage of transfusion requirement after 12 weeks of treatment, comparing patients treated with HEMAX PFS versus those treated with EPREX/ ERYPO®.
- Intragroup efficacy (HEMAX PFS and EPREX/ ERYPO®) of treatment with Epoetin Alfa through increased levels of hemoglobin from baseline in each one of the intermediate visits until the week 12 visit.
- Evaluate the intragroup efficacy (HEMAX PFS and EPREX/ ERYPO®) of the change from the twice - a - week dosing during the titration phase to a weekly dosing during the maintenance phase through the variation of the hemoglobin levels from week 12 to the weeks 16, 20 and 24.

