11.3 CONCOMITANT MEDICATIONS/ TREATMENT OF ANEMIA

Transfusions: Patients will be transfused according to the clinical judgment of the investigator, based on the patient's symptoms and not on a cutoff value of hemoglobin. The transfused patients will be withdrawn from the study for having reached a study endpoint.

Iron intake: All patients will receive concomitant treatment with iron orally to maintain the levels of transferrin saturation >20% according to the indications of the treating physicians. The intravenous iron is also permitted, according to the criterion of the treating physicians.

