12.3.6 Visit 11 (week 24) or end - of - study visit

This visit will be scheduled four weeks after the previous visit with a window of ± 1 week from the respective date.

The following tasks will be carried out in the consultation during this visit:

- Blood pregnancy test (only in women of childbearing potential)
- Samples for full local laboratory test, consisting of:
 - Complete hemogram with reticulocyte and platelet count.
 - Hepatogram,
 - Glycemia, lipid profile (HDL, LDL and triglycerides)
 - Ionogram, calcium, phosphorus, urea and creatinine,
 - Serum iron, transferrin, transferrin saturation, and ferritin
 - Serum sample for antibodies and hepcidin dosage (the sample will be collected and stored for further analysis)
- Pulse, will be measured after the patient has been at rest during 5 minutes.
- Blood pressure: 3 measurements separated by 5 minutes each will be taken, for which the patient should be at rest and sitting. The first measurement will be discarded and the values obtained at the second and third measurements will be averaged, a mean value that will be recorded in the medical history and in the case report form (CRF).
- The prescribed doses of HEMAX PFS or EPREX/ ERYPO® will be recorded, controlling the returned empty boxes and the dose recording cards.
- Medication accounting will be performed
- Adverse events will be recorded and entered in the medical history and in the CRF.

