14 EVALUATION METHODS

14.1 METHODS OF EFFICACY EVALUATION

The following parameters will be evaluated for treatment efficacy, according to the objectives defined by the protocol at each visit:

- Levels of hemoglobin and its variation at each visit, with intragroup and intergroup comparison
- Percentage of responder patients, defined as the increase of Hb ≥ 1 g/ dl without transfusion requirement.
- Number and percentage of patients that require at least one transfusion.

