14.2.7 Full laboratory tests

A full laboratory test will be performed at the baseline visit (week - 1) and at the week 12 and week 24 visits or at study completion visit and all clinically relevant data will be recorded in the source documents of the patient and in the individual case record form (ICRF). Samples for full local laboratory test will consist of:

- Complete hemogram with reticulocyte (through flow cytometry or hematologic counter) and platelet count.
- Hepatogram,
- Glycemia, lipid profile (HDL, LDL and triglycerides)

- Ionogram, calcium, phosphorus, urea and creatinine,
- Serum iron, transferrin, transferrin saturation, and ferritin
- Beta subunit of chorionic gonadotropin only in women of childbearing potential
- Serum/ plasma sample for antibodies and hepcidin dosage (the sample will be collected and stored frozen at - 20° C for further analysis)

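### The responder analysis in SAP 8.2 and Protocol 16.5 omits the no-transfusion condition, and no rule keeps a post-transfusion hemoglobin out of it

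*SAP*

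**What the plan says.** **Two responder definitions.** Protocol 14.1 defines a responder by a rise of at least "1 g/ dl without transfusion requirement", and the endpoint bullet in SAP 3.2.3 carries the same condition. SAP 8.2 begins its endpoint with "Percentage of responder patients (increase of Hb", gives the 1 g/dl threshold and the 12-week timepoint, and stops there. Protocol 16.5, the objectives in both documents and the line directly under the SAP 3.2.3 bullet are worded the same way, without the transfusion condition.

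**What happens to a transfused patient.** Protocol 11.3, repeated in SAP 7.5, states: "The transfused patients will be withdrawn from the study for having reached a study endpoint". Protocol 9.4 lists "Patient transfusion or lack of response after 12 weeks of treatment" among the reasons for leaving, and says: "The termination visit should be performed in all patients that completed the study prematurely". The end-of-study visit (Protocol 12.3.6) includes a "Complete hemogram with reticulocyte and platelet count", and Protocol 14.2.7 places the full laboratory test "at the week 12 and week 24 visits or at study completion visit".

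**Missing data and analysis sets.** Protocol 16.5 and SAP 6.3 fill missing hemoglobin by LOCF. Neither mentions values taken after a transfusion. Protocol 16.5 analyses efficacy in both FAS and PP. SAP 8.1 names the per-protocol population for the primary analysis; SAP 8.2 names none.

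**The concern.** Needing a transfusion is a failure of epoetin treatment, and the plan treats it as an endpoint in its own right. Under the wording of the two analysis sections, the same patient can also be scored as a responder, because the transfusion itself may supply the hemoglobin rise. A programmer working from SAP 8.2 would code the rule without the condition, and no sentence says which definition governs. The two rules classify such a patient in opposite ways, so the reported responder rate depends on which section was followed. The error favours whichever arm has more transfusions. The same unguarded LOCF rule applies to the week 16 to 24 analysis of the switch to weekly dosing.

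**Working it through.** The plan states no expected responder rate or transfusion rate, so there is no figure of its own to reproduce here. The planned 120 patients relate to the primary comparison and do not bear on this point.

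**Step 1. The route.** Transfusion leads to withdrawal, withdrawal to a termination visit, and the termination visit to a hemogram. Since the transfusion causes the withdrawal, that hemogram would ordinarily follow it, although the documents do not fix the order. It is then the last observed hemoglobin, and LOCF carries it forward. In the copy reviewed, the procedures tables show no hemogram mark at the final visit. Their columns may have been disturbed in extraction, and the visit text is explicit.

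**Step 2. Which analysis sets keep the patient.**

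| Set | Entry condition | Patient transfused and withdrawn before week 12 |
|---|---|---|
| Protocol FAS (16.3.1) | randomized, one dose | kept; LOCF fills week 12 |
| Protocol PP (16.3.2) | one dose, one follow-up visit, no major violation | can be kept |
| SAP PP (6.2.1), used for the primary | week 12 visit, no substantial deviation | removed |
| SAP 8.2 | none named | undetermined |

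SAP 7.2 lists the lack of an evaluable week 12 hemoglobin as a deviation that can exclude a patient, but does not list transfusion. With a window of ±7 days (Protocol 12.1), a termination visit close to week 12 could be taken as the week 12 visit. A patient transfused in maintenance has already completed week 12 and stays in every set, so LOCF can carry a post-transfusion value to weeks 16, 20 or 24.

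**Step 3. Responder rate.** If k patients in an arm of n are counted as responders instead of non-responders, the shift is k/n.

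| n | k = 1 | k = 3 |
|---|---|---|
| 60 (planned) | 1.7 points | 5.0 points |
| 23 (HEMAX PFS, enrolled) | 4.3 points | 13.0 points |
| 20 (EPREX/ERYPO, enrolled) | 5.0 points | 15.0 points |

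These are upper bounds. For the transfusion to create the response, the later hemoglobin must be at least 1 g/dl above baseline and the earlier one must not have been. If a transfusion adds r g/dl, the change from baseline before it must lie between 1 − r and 1. Assuming r = 1 to 2 g/dl, that is 0 to 1 g/dl for r = 1 and −1 to 1 g/dl for r = 2.

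The choice of set matters too. Assume an arm of 20 with 14 responders, and 2 of the other 6 transfused:

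- transfused patients counted as non-responders: 14/20 = 70.0%
- excluded, as in the SAP PP: 14/18 = 77.8%
- counted as responders: 16/20 = 80.0%

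**Step 4. Primary mean.** Read the averaging window as weeks 8, 10 and 12, with m of those three visits affected. The shift in the arm mean is (k/n) × r × (m/3). For k = 1, n = 20 and r = 1 to 2 g/dl:

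- only week 12 affected (m = 1): 0.05 × (1 to 2) × 1/3 = 0.017 to 0.033 g/dl
- all three affected (m = 3): 0.05 × (1 to 2) = 0.05 to 0.10 g/dl, possible only under the Protocol's FAS or PP

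**The case against.** The strongest reply is that SAP 3.2.3 is the SAP's endpoints section and defines the responder with the transfusion condition. SAP 8.2 can then be read as shorthand for that endpoint at its timepoint. This is a fair reading, and it means the condition has not been removed from the plan. What remains is an inconsistency: the line under the same bullet and both analysis sections give the endpoint without the condition, and nothing ranks one above the other.

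A reader might also infer more than the documents support:

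- **That the primary equivalence result is seriously contaminated.** The SAP primary uses a per-protocol set that requires the week 12 visit, which removes earlier withdrawals. The larger mean shift arises only under the Protocol's FAS or PP, and even that is small against the margin.
- **That a transfusion after week 12 is counted nowhere.** The general transfusion bullets in Protocol 14.1 and SAP 3.2.3 carry no time limit, and SAP 7.1 reports withdrawals by reason, transfusion included. The maintenance analysis is intragroup, so it does not enter the between-arm equivalence test.
- **That an efficacy deficit would be hidden.** The percentage of patients transfused is compared between arms in the next bullet of SAP 8.2, so an imbalance would be visible there.

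The replies on size also stand: the documents give no transfusion rate, and not every transfused patient would reach the 1 g/dl rise.

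**Conclusion.** The concern holds for the responder endpoint and, within each arm, for the week 16 to 24 hemoglobin analysis. As written, a transfused patient can be scored as a response to epoetin under the Protocol's FAS and PP and in SAP 8.2. Under the definition in Protocol 14.1 that patient is a non-responder in any population. Excluding the patient, as the SAP per-protocol set would for an early withdrawal, does not match 14.1 either, because it removes a failure from the denominator.

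The size is at most 5.0 points per transfused patient at n=20 and 4.3 at n=23, subject to the before-and-after hemoglobin condition above. For the SAP primary analysis only a transfusion close to week 12 can enter. If it raises hemoglobin by an assumed 1 to 2 g/dl and affects week 12 alone, the arm mean moves by about 0.02 to 0.03 g/dl per patient at n=20. This is a correction that should be made to a secondary endpoint and to the hemoglobin data rules. It is not a threat to the primary conclusion.

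**What to change.** - In Protocol 16.5 and SAP 8.2, state the responder definition of Protocol 14.1 in full.
- Count any patient transfused by week 12 as a non-responder and keep that patient in the denominator. Name the population for SAP 8.2 accordingly; the Protocol's FAS would serve, and the SAP would need to define it because 6.2 lists only the per-protocol and safety populations.
- In SAP 6.3 and Protocol 16.5, exclude hemoglobin taken after the first transfusion from all hemoglobin analyses, including the primary and the week 16 to 24 analysis, and from LOCF. Where a value is needed, use the last one before the transfusion.

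No new endpoint is needed for transfusion during maintenance; scoring it as a failure of weekly dosing would go beyond the planned analysis.

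The cost is SAP wording, a matching amendment to Protocol 16.5 (approved as Protocol 17.4 requires), and one comparison of the transfusion date with the sample date. No new assessments are needed, assuming the transfusion date is on record, as it should be for an event that triggers withdrawal. The responder rate may come out slightly less favourable.
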